12.2 Withdrawal of Patients from the Study

Participation of a patient will be discontinued in the event that:

- An AE or SAE that, in the judgment of the Investigator, requires treatment withdrawal due to its nature, severity, or required treatment, regardless of the causal relationship to treatment
- Protocol violations, including non-compliance, loss to follow-up

- Occurrence of an exclusion criterion that is clinically relevant and affects the patient's safety, if discontinuation is considered necessary by the Investigator and/or Sponsor
- Serum transaminases (ALT and/or AST) $>3 \times$ upper limit of normal (ULN) AND total bilirubin $>2 \times$ ULN (confirmed by subsequent repeat) without an alternative explanation
- Elevation of ALT or AST $>3 \times$ ULN (confirmed by repeat) with the appearance or worsening of symptoms felt by the Investigator to be potentially related to hepatic inflammation, such as fatigue, nausea, vomiting, right upper quadrant pain or tenderness, fever, rash, or eosinophilia
- Use of a non-permitted concomitant drug, as defined in [Section 7.1](#)
- Withdrawal of the patient's consent
- Participation in any other trial during the duration of this trial
- Loss of ability to freely provide consent through imprisonment or involuntary incarceration for treatment of either a psychiatric or physical (e.g., infectious disease) illness
- Discretion of the Investigator

All patients are free to withdraw from participation at any time for any reason specified or unspecified, and without prejudice.

Reasonable attempts will be made by the Investigator to provide a reason for patient withdrawals. The reason for the patient's withdrawal from the study will be specified in the patient's source documents. As noted above, patients who discontinue study treatment early (i.e., they withdraw prior to Day 168) should have an ET visit. Refer to [Table 1](#) for ET procedures. Patients who withdraw after Day 84 but prior to Day 168 should be encouraged to come in for a final visit.

12.3 Replacement of Patients

Patients who do not meet all eligibility criteria at Screening or who qualify at Screening but do not enter the Run-in period within 6 weeks may be rescreened once and assigned a new Screening number.

Patients who withdraw prematurely from the study will not be replaced.

13 PROTOCOL VIOLATIONS

A protocol violation occurs when the patient, Investigator, or Allakos, Inc., fails to adhere to protocol requirements affecting the inclusion or exclusion criteria, patient safety, or primary endpoint. Protocol violations for this study include, but are not limited to, the following:

- Failure to meet inclusion/exclusion criteria
- Use of a prohibited concomitant medication

- Failure to comply with GCP guidelines will also result in a protocol violation

Allakos, Inc., will determine if a protocol violation will result in withdrawal of a patient.

When a protocol violation occurs, it will be discussed with the Investigator and a Protocol Violation Form detailing the violation will be generated. This form will be signed by a Sponsor representative and the Investigator. A copy of the form will be filed in the investigational site's regulatory binder and in the Sponsor's files.

14 DATA SAFETY MONITORING

14.1 General Safety Monitoring

The Sponsor's Medical Monitor will review data relating to safety and to the conduct of the study as it becomes available.

14.2 Data Monitoring Committee

A DMC will be convened periodically to monitor the safety of patients over the course of the study. Members of the DMC can request the identities of patients' study drugs if needed. Other information about the DMC can be found in the DMC charter.

14.3 Study Stopping Rules

The trial must be discontinued prematurely in the event of any of the following:

- A life-threatening adverse event that is possibly or probably related to treatment
- A fatal adverse event that is possibly or probably related to treatment
- New information leading to unfavorable risk-benefit judgment of the study drug, e.g., occurrence of significant previously unknown adverse reactions, unexpectedly high intensity or incidence of known adverse reactions, or other unfavorable safety findings
- >25% of patients at any time have been withdrawn due to drug-related AEs, including those related to abnormal laboratory results, or other safety findings
- Sponsor's decision that continuation of the trial is unjustifiable for medical or ethical reasons
- Poor enrollment of patients making completion of the trial within an acceptable time frame unlikely
- Discontinuation of development of the Sponsor's study drug

Regulatory Authorities and IRBs/IECs will be informed about the discontinuation of the trial in accordance with applicable regulations. The trial may be terminated or suspended upon request of Regulatory Authorities.

15 STATISTICAL METHODS AND CONSIDERATIONS

This section outlines the nature and rationale for the statistical methods to be used for the analysis of the data from the study. Baseline will be defined as the last measurement before the patient is randomized. All data will be included in data listings. A separate Statistical Analysis Plan (SAP), which must be documented as completed prior to unblinding the study, will describe data handling and statistical techniques in full detail, except missing PK data handling and PK analysis methods will be described in the PK report. The SAP will contain any modifications to the analysis plan described below in this section.

15.1 Analysis Populations

15.1.1 Safety Population

All safety analyses will be performed in the Safety Population, defined as all patients who were randomized and received at least 1 dose of the study drug. Patients will be analyzed according to the study drug they received.

15.1.2 Pharmacokinetics Population

The PK analysis of AK001 will be performed in the PK Population, defined as patients with serum concentration data obtained at pre-defined time points.

15.1.3 Efficacy Populations

The main population for efficacy will be the Modified Intention-to-Treat Population, defined as all patients randomized who receive at least 1 dose of study drug and have a valid Baseline measurement and at least 1 post-baseline efficacy assessment. Patients will be analyzed for efficacy according to the group to which they were randomized.

In addition, the primary efficacy analyses will also be performed for the Per-Protocol Population, defined as patients who have a Week 12 visit and valid efficacy measurements.

15.2 Demographic and Baseline Characteristics

Demographic and Baseline variables that will be summarized by treatment and dose group include:

- Demographics
- Medical history
- Complete PE
- Safety variables including vital signs and laboratory tests (including chemistries, hematology, and urinalysis) obtained at Screening, and ADA obtained on Day 0 pre-dose

15.3 Analysis of Primary Endpoint

The effect of 2 different dose levels of AK001 in combination with an INS versus the INS alone on the reduction in size of nasal polyps as evaluated by the change from Baseline to

Week 12 after the start of treatment in TPS (Appendix 2 [Section 19.2](#)) will be displayed for each treatment group by study visit using summary statistics, including the number of observations, the mean, median, standard deviation (SD), and range. Each active treatment group will be compared separately with the placebo group for change from Baseline in TPS by using a mixed effect repeated measures analysis of variance (ANOVA) model with specific contrast statement for Week 12 and for each comparison separately. Adjustment in alpha for multiple comparisons will be controlled according to the Hochberg method, in which, if the efficacy comparison of the high active arm versus placebo is statistically significant at the 0.05 level, no penalty will be assessed to the comparison of the low active arm versus the placebo arm. Otherwise, the low active arm versus the placebo arm will be compared at the 0.025 level.

Missing values for the primary endpoint will be imputed by 2 methods: last observation carried forward and worst observation carried forward. Imputations will be done on the total score level and not on the individual item level. Due to the sample size, no multiple imputation technique is intended.

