6.2 Inclusion Criteria

Patients are eligible for the study if all of the following criteria are met:

1. Written informed consent
2. Male and female patients aged ≥ 18 and ≤ 75 years at the time of Screening
3. SNOT-22 (Appendix 5 [Section 19.5](#)) ≥ 30
4. At Screening, TPS of ≥ 5 for both nostrils with presence on endoscopy of nasal polyps of grade ≥ 2 in each nostril according to the polyp grading scale (Appendix 2 [Section 19.2](#))
Polyp grading scale for each nostril:
0=no nasal polyps
1=small polyps in the middle meatus not reaching below the inferior border of the middle turbinate
2=polyps reaching below the lower border of the middle turbinate
3=large polyps reaching the lower border of the inferior turbinate or polyps medial to the middle turbinate
4=large polyps causing complete obstruction of the inferior nasal cavity
5. History of at least 2 of the following symptoms for 4 weeks prior to Screening:
 - a) Anterior nasal discharge
 - b) Posterior nasal discharge
 - c) Nasal congestion, blockade, or obstruction

- d) Decreased sense of smell
- e) Facial pain or pressure
- 6. Received continuous topical nasal steroids and/or leukotriene receptor antagonists for at least 8 weeks prior to Screening unless failure or no effect of prior nasal steroid or leukotriene receptor antagonist therapy is documented
- 7. At randomization, received $\geq 80\%$ of doses of NASONEX scheduled during the Run-in period
- 8. At randomization, TPS of ≥ 5 for both nostrils with presence on endoscopy of nasal polyps of grade ≥ 2 in each nostril according to the polyp grading scale (see Inclusion Criterion #4 and Appendix 2 [Section 19.2](#)) and despite prior INS treatment during the Run-in period
- 9. Female patients must be post-menopausal for ≥ 1 year with documented follicle-stimulating hormone (FSH) > 30 IU/L, surgically sterile (tubal ligation, hysterectomy, or bilateral oophorectomy) for at least 3 months, or, if of child-bearing potential, willing to use a highly effective method of contraception (Appendix 1 [Section 19.1](#)) from Screening until at least 17 weeks after the last dose of the study drug is administered, which corresponds to approximately 5 half-lives of AK001

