15.4 Analysis of Secondary Endpoints

Additional efficacy measures will be analyzed in support of the primary efficacy endpoint results.

In addition to change from Baseline in TPS (Appendix 2 [Section 19.2](#)), absolute values and percentage changes from Baseline will be analyzed separately using the same repeated measures model described above. A responder analysis will also be considered. The response definition and its appropriate analysis methodology will be presented in the SAP. The numbers (percentages) of patients who are responders and time to first response for each active treatment group will be compared separately with the placebo group, if feasible.

Examination of the treatment effect over time for TPS (Appendix 2 [Section 19.2](#)), UPSIT (Appendix 4 [Section 19.4](#)), and patient-reported symptoms of sinusitis (SNOT-22) (Appendix 5 [Section 19.5](#)) will be examined using an appropriate similar repeated measures ANOVA. The stratification factor, presence or absence of asthma, may be included in the model. The details of the analytical methods will be presented in the SAP.

Size of polyps as evaluated by Lund-Mackay score (Appendix 3 [Section 19.3](#)) at selected Investigator sites by CT scan (CT scans are optional and will only be done at Investigator sites at which appropriate and timely regulatory approval or authorization can be granted); PNIF; UPSIT (Appendix 4 [Section 19.4](#)); and patient-reported SNOT-22 (Appendix 5 [Section 19.5](#)), VAS (Appendix 6 [Section 19.6](#)), clinical symptoms improvement scale³ (Appendix 6 [Section 19.6](#)), and SF-36 (Appendix 7 [Section 19.7](#)) scores for each active treatment group will be compared separately with the placebo group using a repeated measure ANOVA with contrast statements for comparison at Week 12 as well as other time points in the study.

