15.5 Analysis of Exploratory Endpoints

The exploratory analyses are not powered for statistical significance.

Potentially, markers of MCs and eosinophils and inflammatory response in blood for each active treatment group will be compared separately with the placebo group, with suitable analyses that will be described in the SAP.

Enrollment in this study is designed for presence or absence of asthma as a stratification factor; thus, asthma will be equally distributed among the 3 groups. This stratification factor may be used in the analyses of the primary and secondary analyses described above. Additional exploratory analyses are planned to explore any possible trend in favor of AK001 in the subgroup of asthmatic patients.

In patients with comorbid asthma, use of asthma rescue therapy will be summarized by number and percentage. Changes from Baseline; percentage changes from Baseline; absolute TPS (Appendix 2 [Section 19.2](#)); pulmonary function (assessed using spirometry) as evaluated by FEV1, FVC, FEF; and ACT (Appendix 8 [Section 19.8](#)) for each active treatment group will be compared separately with the placebo group using the same repeated measures model described above, to detect any potential trend at Week 12 and at other visits.

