15.7 Sample Size and Randomization

The study will be conducted at approximately 14 investigational sites in the European Union and the United States, and approximately 70 patients will be enrolled.

This study will evaluate the effect of 2 different dose levels of AK001 in combination with an INS versus the INS plus placebo on the reduction in size of nasal polyps. Assuming equal efficacy effect of the 2 active treatment arms, a planned sample size of approximately 70 patients (25 mg of AK001 [n=25], 250 mg of AK001 [n=25], and a corresponding placebo (n=20)) will ensure at least 80% power to detect a difference in mean nasal polyp scores between the placebo group (Mean= -0.3; SD ≤ 1.128) and each of the AK001 groups (Mean= -1.9; SD ≤ 2.064) with an alpha of 0.05. PASS 11, Version 11.0.10, was used for this power analysis.

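### Free improvement: the primary model for Week 12 change in TPS names no Baseline TPS covariate, which gives up some precision and leaves part of any chance Baseline difference in the contrast

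*Protocol*

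**What the plan says.** Section 15.3 of the protocol sets the primary comparison of each active arm with placebo as an analysis of "change from Baseline in TPS by using a mixed effect repeated measures analysis of variance (ANOVA) model with specific contrast statement for Week 12". It lists no covariates.

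Section 15.4 adds that "absolute values and percentage changes from Baseline will be analyzed separately using the same repeated measures model described above".

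The only covariate named for any efficacy model is the asthma stratum, and it is optional. Section 15.5 says: "This stratification factor may be used in the analyses of the primary and secondary analyses described above". Section 15.4 says much the same for the analyses over time.

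The introduction to Section 15 defines the reference value: "Baseline will be defined as the last measurement before the patient is randomized". For TPS this is the centrally read endoscopy of Day -3 (Section 9.6.3). The main efficacy population already requires a valid Baseline (Section 15.1.3).

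The same introduction says that a separate SAP "will describe data handling and statistical techniques in full detail", and adds: "The SAP will contain any modifications to the analysis plan described below in this section".

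**The concern.** Change in TPS probably depends on where a patient starts. The score runs from 0 to 8, and entry requires "At randomization, TPS of ≥ 5 for both nostrils" (Section 6.2), after the same threshold at Screening. A patient at 8 cannot worsen, and selection above a cut-off invites regression to the mean. Subtracting Baseline handles this fully only if change is unrelated to Baseline.

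Randomization is stratified by asthma alone (Section 8.1). The design therefore does not balance Baseline TPS across arms of 20 and 25.

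If change does depend on Baseline, a model without it has a wider confidence interval than the same data allow, and its Week 12 contrast carries part of any chance Baseline difference between arms.

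**Working it through.** **Step 1. Reproduce the planned power, with no Baseline term.**

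Inputs from Section 15.7: placebo "Mean= -0.3; SD ≤ 1.128", n = 20; each AK001 arm mean -1.9, SD 2.064, n = 25; alpha 0.05, taken as two-sided. The difference is 1.6. No dropout is assumed.

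- Variance of the contrast = 1.128²/20 + 2.064²/25 = 0.06362 + 0.17040 = 0.23402
- SE = √0.23402 = 0.484; Welch df = 38.5
- Power (noncentral t) = 89.7% at 0.05 and 83.1% at 0.025, the level that Section 15.3 applies to the low dose if the high dose fails

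A pooled-SD t test (SD 1.715) gives 86.0% at 0.05 and 78.2% at 0.025. The protocol states its power at 0.05, so its figure of at least 80% is met either way.

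**Step 2. Does the text imply an unadjusted model?**

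Write Y for Week 12 TPS and B for Baseline TPS, so that change = Y - B. If B is a covariate, replacing Y by Y - B lowers the coefficient of B by 1 and leaves the treatment contrast unchanged. Analyzing absolute values and change separately with one common model, as Section 15.4 plans, can give two different contrasts only if B is not in that model. The wording therefore points to an unadjusted model but does not prove it.

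**Step 3. What adjustment would gain.**

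Let b be the slope of change on Baseline and s the Baseline SD. Adjustment removes b²s² from the variance of change in each arm. The documents give neither b nor s, so both are assumptions. With s = 1.0 and b = -0.5, b²s² = 0.25:

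- Placebo: (1.2724 - 0.25)/20 = 0.05112
- AK001: (4.2601 - 0.25)/25 = 0.16040
- Sum = 0.21152; ratio 0.21152/0.23402 = 0.904; SE = 0.460
- Power = 92.3% at 0.05 and 86.8% at 0.025

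Range for s from 0.8 to 1.2:

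| Slope b | Fall in variance | Power at 0.05 |
|---|---|---|
| 0 | 0% | 89.7% |
| -0.2 | 1% to 2% | 90.0% to 90.3% |
| -0.5 | 6% to 14% | 91.4% to 93.4% |

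**Step 4. What chance imbalance carries.**

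The SD of the Baseline difference between two arms is s√(1/20 + 1/25) = 0.3s. This is 0.30 points for s = 1.0, and 0.24 to 0.36 for s from 0.8 to 1.2. The unadjusted change contrast carries b times that difference: 0.5 × 0.30 = 0.15 points, or 9% of the planned 1.6. Its square, 0.0225, is the variance removed in Step 3 (0.23402 - 0.21152). The imbalance and the lost precision are therefore one quantity and should not be counted twice.

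**The case against.** The strongest reply is that Section 15.3 names a model class, an outcome and a contrast, not a full list of terms. It does not list treatment or visit effects either. Covariates are commonly left to the SAP, Section 15 defers full detail to it, and no sentence excludes Baseline TPS. This stands as far as it goes: nothing in the protocol is wrong or contradictory here. It does not remove the point, because Section 15.4's separate test of absolute TPS with the same model makes sense only without Baseline.

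Stronger readings are tempting, but the documents do not support them:

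- **That the primary comparison is biased or underpowered.** Treatment is randomized, so chance imbalance is noise already counted in the standard error. The stated power is met without adjustment.
- **That adjustment is worth up to a third more patients.** This needs a Baseline-change correlation of -0.5, since 1/(1 - 0.25) = 1.33. With Baseline SD 0.9 to 1.1 and the AK001 SD of 2.064, the slope would be -0.5 × 2.064/1.1 = -0.94 to -0.5 × 2.064/0.9 = -1.15. Week 12 TPS would then be nearly unrelated, or inversely related, to Baseline TPS. Because entry restricts Baseline to 5 to 8, the gain may well be at the low end.
- **That leaving Baseline out hurts the absolute-value analysis more.** Absolute TPS carries (1 + b) times the Baseline difference and change carries b times it. The first is larger in size only if the slope is shallower than -0.5, and the documents do not give the slope.

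**Conclusion.** The point holds as a free improvement, not as an error. The protocol names no Baseline TPS covariate, and Section 15.4 suggests that none is intended; the SAP may already settle it. The likely gain is modest: about 10% less variance and power of about 92% instead of 89.7%, if Baseline SD is 1.0 and the slope of change on Baseline is -0.5. It falls to nothing at slope 0. These figures also assume a two-sided Welch comparison, no dropout and the same slope in each arm. The reading of the text is firm; the size of the gain rests on assumptions.

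**What to change.** In Section 15.3, or in the SAP before unblinding, add Baseline TPS and Baseline TPS by visit as covariates in the primary repeated measures model. Use the same model for TPS in Section 15.4. Adjusted change and adjusted absolute TPS then give the same treatment contrast, so the separate absolute-value test is redundant and can be dropped; absolute means can still be tabulated. Percentage change is a different outcome and is not covered by this equivalence.

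The cost is one sentence and a few degrees of freedom. Baseline TPS is already collected and already required for the main efficacy population, so no data or visits are added. If the SAP already contains these terms, nothing more is needed than aligning the wording of 15.3 and 15.4.

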	
nasal polyps as evaluated by the change from Baseline to Week 12 after the start of treatment in TPS will be displayed for each treatment group by study visit, using summary statistics including the number of observations, the mean, median, SD, and range. Each active treatment group will be compared separately with the placebo group for change from Baseline in TPS by utilizing a mixed effect repeated measures analysis of variance (ANOVA) model with specific contrast statement for Week 12 and for each comparison separately. Adjustment in alpha for multiple comparison will be controlled according to the Hochberg method, in which, if the efficacy comparison of the high active arm versus placebo is statistically significant at the 0.05 level, no penalty will be assessed to the comparison of low active arm versus placebo. Otherwise, the low active arm versus placebo will be compared at the 0.025 level.
 
Additional efficacy measures will be analyzed in support of the primary efficacy endpoint results.
 
In addition to change from Baseline in TPS, absolute values and percentage changes from Baseline will be analyzed separately using the same repeated measures model described above. A responder analysis will also be considered.
 
Examination of treatment effect over time for TPS, UPSIT, and patient-reported symptoms of sinusitis (SNOT-22) will be examined using appropriate similar repeated measures ANOVA. The stratification factor, presence or absence of asthma, may be included in the model.
 
Size of polyps as evaluated by Lund-Mackay score at selected Investigator sites by CT scan (the CT scans are optional and will only be done at Investigator sites at which appropriate and timely regulatory approval or authorization can be granted); PNIF; UPSIT; and patient-reported SNOT-22, VAS, clinical symptoms improvement scale, and SF-36 scores will be compared between each of the 2 active treatment groups and the placebo group using a repeated measure ANOVA with contrast statements for comparison at Week 12 as well as at other time points in the study.

--	---

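### The multiplicity rule for the primary endpoint is called Hochberg, but as written it tests 250 mg at 0.05 unconditionally; taken literally, family-wise error is about 7% when neither dose works

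*Protocol*

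**What the plan says.** Protocol Section 15.3 makes two comparisons on the primary endpoint, the Week 12 change in Total Polyp Score: "Each active treatment group will be compared separately with the placebo group for change from Baseline in TPS". It names the multiplicity method: "Adjustment in alpha for multiple comparisons will be controlled according to the Hochberg method". The same sentence goes on, as the content of that method, that "if the efficacy comparison of the high active arm versus placebo is statistically significant at the 0.05 level, no penalty will be assessed" to the 25 mg comparison. The next sentence covers the other case: "Otherwise, the low active arm versus the placebo arm will be compared at the 0.025 level". The Statistics part of the synopsis gives the same method ("Adjustment in alpha for multiple comparison will be controlled according to the Hochberg method") and the same dose-ordered rule.

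Two other places bear on the point. Section 15 says of the SAP: "The SAP will contain any modifications to the analysis plan described below in this section". Section 15.7 claims that 25, 25 and 20 patients (25 mg, 250 mg, placebo) "will ensure at least 80% power to detect a difference in mean nasal polyp scores" for each dose against placebo, at an alpha of 0.05.

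**The concern.** With two comparisons, Hochberg's procedure orders the p-values, not the doses. If the larger p-value is at most 0.05, both comparisons succeed. If not, only the smaller is considered, and it must be at most 0.025. Either dose can hold either position.

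The protocol's rule is ordered by dose. It treats 250 mg as significant at 0.05 and attaches no condition on 25 mg. It is not a fixed sequence either, because 25 mg keeps a 0.025 route after 250 mg has failed. The literal rule therefore spends 0.05 on 250 mg and, when that fails, a further 0.025 on 25 mg.

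The named method and the written rule can give opposite verdicts on the primary endpoint. With p=0.04 for 250 mg and p=0.20 for 25 mg, the written rule declares 250 mg effective and Hochberg declares nothing. A prespecified rule should not leave that choice open, and the literal version lacks the 5% family-wise control that the name implies.

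**Working it through.** **Inputs.** Arm sizes are 20 (placebo), 25 and 25. Planning means are −0.3 for placebo and −1.9 for each dose, with SDs 1.128 and 2.064 and alpha 0.05 (Section 15.7). Test levels are 0.05 and 0.025 (Section 15.3). Sidedness is not stated; two-sided is assumed, with critical values 1.960 (0.05) and 2.241 (0.025).

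**1. The protocol's power figure.**
- SE = √(1.128²/20 + 2.064²/25) = √(0.0636 + 0.1704) = 0.4838, and 1.6/0.4838 = 3.307.
- Normal approximation: Φ(3.307 − 1.960) = 91.1%. Unequal-variance t: 89.7%. Two-arm pooled SD (1.715): 87.5%.
- At alpha 0.025 the same three are 85.7%, 83.1% and 80.8%.

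The stated minimum of 80% is reproduced.

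**2. Where the two rules differ.**

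| p (250 mg) | p (25 mg) | Written rule | Hochberg |
|---|---|---|---|
| ≤0.025 | ≤0.05 | both | both |
| ≤0.025 | >0.05 | 250 mg | 250 mg |
| 0.025 to 0.05 | ≤0.05 | both | both |
| **0.025 to 0.05** | **>0.05** | **250 mg** | **none** |
| >0.05 | ≤0.025 | 25 mg | 25 mg |
| >0.05 | >0.025 | none | none |

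Only the fourth row differs, and only for 250 mg. The 25 mg verdict is identical throughout.

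**3. Family-wise error when neither dose works.** The two contrasts share the placebo arm. Their correlation is
- equal SDs: (1/20)/(1/20 + 1/25) = 0.05/0.09 = 0.556;
- planning SDs: 0.0636/(0.0636 + 0.1704) = 0.272.

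Written rule: 1 − P(|Z₂₅₀| < 1.960 and |Z₂₅| < 2.241). Hochberg: P(both p ≤ 0.05, or smaller p ≤ 0.025). Excess D = P(0.025 < p₂₅₀ ≤ 0.05 and p₂₅ > 0.05).

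| Correlation | Written | Hochberg | D |
|---|---|---|---|
| 0.556 | 6.83% | 4.75% | 2.08% |
| 0.272 | 7.25% | 4.95% | 2.30% |
| 0 | 7.375% | 5.00% | 2.375% |

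The last row can be done by hand. Written: 1 − 0.95 × 0.975 = 0.07375. D: 0.025 × 0.95 = 0.02375. Hochberg: (1 − 0.975²) + 0.025² = 0.049375 + 0.000625 = 0.05. In every row the written rule equals Hochberg plus D.

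**4. Simulation** (1,000,000 trials per scenario). With neither dose effective, equal SDs and a pooled t test, the written rule gives 6.8% and Hochberg 4.7%. With planning SDs and unequal-variance t tests the figures are 7.2% and 4.9%. The 25 mg verdicts never differed in any scenario.

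**5. One or both doses effective** (planning values, unequal-variance t).

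| Scenario | Quantity | Written | Hochberg | Fixed sequence |
|---|---|---|---|---|
| Both work | 250 mg power | 89.7% | 88.6% | 89.7% |
| Both work | 25 mg power | 88.6% | 88.6% | 81.4% |
| Only 250 mg works | 250 mg power | 89.7% | 83.3% | 89.7% |
| Only 250 mg works | false 25 mg claim | 4.6% | 4.6% | 4.3% |
| Only 25 mg works | 25 mg power | 83.3% | 83.3% | 4.3% |
| Only 25 mg works | false 250 mg claim | 5.0% | 4.6% | 5.0% |

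The two rules disagree on 250 mg in 89.66 − 88.62 = 1.0% of trials if both doses work, and in 89.66 − 83.34 = 6.3% if only 250 mg works.

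**6. Sensitivity to the variance model.** With planning SDs and one variance pooled over all three arms, the error with neither dose effective is 3.6% (written) and 2.2% (Hochberg). With both doses effective, Hochberg power is 82.3% for each dose and fixed-sequence power for 25 mg is 73.2%. With only 250 mg effective, Hochberg power for 250 mg is 75.2%.

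**The case against.** The strongest reply is that the sentence never states a success rule for 250 mg. It states only what penalty 25 mg carries, and that part is exactly Hochberg. Since the method is named, a statistician would apply it and obtain 4.7% to 5.0%; on this reading the text is an incomplete description that leaves out the mirror condition for 250 mg. That reading is possible, and for this reason 7% is the error of the literal rule and not an established property of the trial. But the protocol presents the clause as what the method consists of, and nothing in it tells the reader that 250 mg can also face 0.025.

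Second, the SAP may restate the procedure. It may, and Section 15 permits that, but the SAP is not available here. The point concerns what the protocol states, not something it leaves out.

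Third, the consequence is narrow. This is true: the excess arises only when neither dose works, and under the planning assumption of two equally effective doses the rules disagree in about 1% of trials. In a 70-patient Phase 2 study this is moderate, not critical.

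Fourth, a repeated-measures model with one common variance would give 3.6% for the written rule if the arms truly differed in variance as planned. That is correct, but it comes from conservative tests under a misspecified variance. It does not make the rule valid, and the same model with equal variances gives 6.8%.

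**Conclusion.** The concern holds. The label and the rule in Section 15.3 and the synopsis do not agree, and the rule as written is neither Hochberg nor a fixed sequence. Taken literally, it gives a family-wise error of 6.8% to 7.4% when neither dose works, 2.1 to 2.4 points above true Hochberg. The whole excess consists of 250 mg claims with p between 0.025 and 0.05 while 25 mg has p>0.05.

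This rests on the literal reading, two-sided tests and a variance model that gives tests of correct size. Using the same levels one-sided gives 6.6% to 7.4%. The text should be corrected before unblinding; the design, sample size and conduct are unaffected.

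**What to change.** Replace the rule in Section 15.3 and in the synopsis, and carry the same text into the SAP. Preferred, because it is the method already named:

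> Hochberg: if both comparisons have p≤0.05, both are significant; otherwise only a comparison with p≤0.025 is significant, whichever dose it is.

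The cost is one sentence in two places. With unequal-variance tests at the planning values, 250 mg power falls from 89.7% to 88.6% if both doses work and from 89.7% to 83.3% if only 250 mg works. Power for 25 mg does not change. When both doses work, the stated 80% is still met for each dose, also with a pooled variance (82.3%).

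A fixed sequence (250 mg at 0.05, then 25 mg at 0.05 only if 250 mg succeeds, otherwise stop) is also valid if the word Hochberg is removed. It is a change of strategy rather than a correction of wording, since it removes the fallback for 25 mg. If both doses work, 25 mg power falls from 88.6% to 81.4% with unequal-variance tests, and is 73.2%, below the stated 80%, with a pooled variance. If only 25 mg works, its power falls from 83.3% to 4.3%. The Hochberg wording is the one to adopt.
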